3.4 Clinical Hypothesis

CBD can act as both a CYP inhibitor and inducer in human hepatocytes in vitro. Therefore, the potential for PK interactions with other drugs that are metabolized by CYP450 enzymes exists. The hypothesis is that the in vivo PK of CLB and its major metabolite (N-CLB) may be altered (increased or decreased) by the chronic administration of GWP42003-P.

4. EXPERIMENTAL PLAN

4.1 Study Design

This phase 2, placebo-controlled study consists of a 34 day, double-blind phase followed by an optional maximum one year OLE. Patients will continue to take CLB

as advised by their physician for the duration of the study. GWP42003-P/placebo will be taken twice daily immediately after their CLB dose.

Patients will enter the study and begin a 10 day GWP42003-P or placebo titration phase. During this period patients will be up-titrated to a maintenance dose or equivalent of 20 mg/kg/day. Patients will continue to take this maintenance dose of GWP42003-P or placebo for 21 days (Days 12 to 32).

Upon completion of the treatment period (Day 34) patients will be invited to receive GWP42003-P during the OLE phase. If a patient enters the OLE they will take GWP42003-P as advised by the investigator. If a patient chooses not to enter the OLE, and/or the investigator does not feel it is in their best interests, they will taper off their GWP42003-P/placebo treatment by reducing their maintenance dose by 10% per day until dosing has ceased. For those patients not entering the OLE, dosing will end on Day 43 and they will receive a telephone follow-up visit four weeks after the end of GWP42003-P/placebo dosing (Day 71).

PK samples will be taken on two occasions during the blinded phase of the study:

- Day 1 (Visit 2) before beginning treatment (patients will be taking CLB only).
- Day 33 (Visit 4) following 21 days of GWP42003-P or placebo maintenance (patients will be taking CLB and GWP42003-P or placebo).

Ten samples will be taken during each PK assessment. PK samples should be taken at time points in respect to the morning dose of CLB. The time points are as follows: Pre-dose, 15min, 30min, 1h, 1.5h, 2h, 4h, 6h, 12h and 24h. PK samples will be quantitatively analyzed for CLB, N-CLB, CBD, CBD major metabolites, THC and THC major metabolites.

Patients should try to be consistent in the timing of their food intake in relation to dosing throughout the blinded phase of the study.

Upon entry into the OLE the dose of GWP42003-P and other AEDs may be adjusted up or down to a maximum of 30 mg/kg/day. The OLE will last for a maximum of one year or until marketing authorization is granted; whichever is earlier.

Patients will be required to keep a paper diary to note the time and dose of IMP and CLB administration each morning and evening and to record any AEs that may occur whilst receiving IMP and any other medications. Patients will also be required to record the number and type of seizures for each day whilst on the study.

A study schema ([Figure 1-1](#)), presented at the end of [Section 1](#), depicts the overall study design. More detailed information on treatment and study procedures are provided in [Section 8](#) and [Section 9](#) respectively.

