3.3.1 Selection of Study Doses

Doses up to 800 mg GWP42003-P per day for up to eight weeks have been well tolerated in adults in GW Research Ltd (GW) clinical study GWMD09112, which, assuming an average weight of 70 kg, equates to a daily dose of 11.4 mg/kg. In the literature, doses of GWP42003-P have been given up to 1500 mg GWP42003-P per day for four weeks in adults, which, in a 70 kg human equates to a daily dose of 21.4 mg/kg GWP42003-P.

Data on the safety of GWP42003-P is emerging from the physician-initiated Epidiolex[®] Expanded Access Program being conducted in the USA. This program has been running since January 2014 and at the time of writing had data on 63 patients. The mean maximum exposure achieved in this patient population of refractory epilepsies was a daily dose of 24.4 mg/kg (n=59 patients) with a maximum dose of 51 mg/kg in one patient. Please see below for a break-down of the groups:

- ≤ 20 mg/kg GWP42003-P n=13 (21%)

- >20 mg/kg - ≤30 mg/kg GWP42003-P n=40 (64%)
- >30 mg/kg - ≤40 mg/kg GWP42003-P n=4 (6%)
- >40 mg/kg GWP42003-P n=2 (3%)
- Dose not reported n=4(6%)

Eleven patients had a daily GWP42003-P dose of >25 mg/kg, of which five did not report any adverse events (AEs). Of note, the patient who received 51 mg/kg did not have any AEs at this dose. The remaining six patients experienced AEs as documented in the [Table 3.3.1-1](#) below:

Table 3.3.1-1 Epidiolex Adverse Events	
Adverse Event Term	Number of Events
Loose stools / urgent bowel movements	2
Increase in seizures	2
Drowsiness	1
Aspiration pneumonia	1
Lethargy	1
Decreased appetite	1
Dyskinesia	1
Urinary tract infection	1

Based on the above, a daily dose up to 20 mg/kg/day (given as two divided doses) has been selected for the GWP42003-P dose in the current study, including a titration period with daily increments of 2.5 mg/kg and 5 mg/kg. At the end of the treatment period, patients will be given the option of continuing onto an open label extension (OLE) period if the investigator and patient both agree that it is in their best interest. During the OLE doses may be adjusted up or down, dependent on investigator opinion, to a maximum daily dose of 30 mg/kg GWP42003-P.

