8.1.2 Dose Escalation and Dose Adjustments

Patients will enter the blinded phase of the study and will be up-titrated over ten days (Day 2 to Day 11) to a maintenance dose or equivalent of GWP42003-P/placebo of 20 mg/kg/day. If GWP42003-P is not tolerated then the dose can be reduced accordingly at the discretion of the investigator. The titration regimen is described in [Table 8.1.2-1](#).

Table 8.1.2-1 Dose Up-Titration Regimen*		
Day - GWP42003-P/Placebo (Blinded Period)	Day - GWP42003-P only (OLE**)	Dose Level (GWP42003-P or equivalent placebo)
2	34	2.5 mg/kg
3	35	2.5 mg/kg
4	36	5.0 mg/kg
5	37	5.0 mg/kg
6	38	7.5 mg/kg
7	39	7.5 mg/kg
8	40	10.0 mg/kg
9	41	10.0 mg/kg
10	42	15.0 mg/kg
11	43	15.0 mg/kg
12 onwards	44 onwards	20.0 mg/kg

*GWP42003-P /placebo is to be taken twice daily. Total daily doses are shown.

** Only patients who were taking placebo during the double-blind period will up-titrate according to this schedule during the OLE period. Those taking GWP42003-P during the double-blind period will down-titrate their blinded IMP whilst simultaneously up-titrating with GWP42003-P, thus maintaining a daily dose of 20 mg/kg/day GWP42003-P throughout.

The titration regimen defined above should be followed to the maximum dose (20 mg/kg/day). Should an AE occur during titration which is attributable to IMP or concomitant AED, then IMP dose should be reduced to the next lower dose. Any other changes in concomitant AED therapy should be reviewed with the medical monitor before being initiated.

For those patients who do not enter the OLE the dose of GWP42003-P/placebo will taper off over 10 days beginning on Day 34. The patient will reduce the dose by 10% of the maintenance dose each day and treatment will end on Day 43.

Patients who enter the OLE period will be transitioned to the OLE treatment over a 10-day period in order to maintain blinding, simultaneously down-titrating blinded GWP42003-P /placebo whilst up-titrating open-label GWP42003-P. As such, patients who were taking GWP42003-P during the blinded period will maintain their 20 mg/kg/day dose throughout the transition from the blinded period into the OLE period and patients who received placebo during the blinded period up-titrate slowly to the 20 mg/kg/day dose in the OLE period. After this has taken place, the

maintenance dose of GWP42003-P may be adjusted up or down at the discretion of the investigator to a maximum of 30 mg/kg/day (no minimum).

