8.2 Concomitant Therapy

Doses of any concomitant AEDs, including CLB, must have been stable for at least four weeks prior to screening and must remain stable throughout the blinded phase of the study. If there are symptoms of toxicity suspected to be from a drug interaction, the investigator may adjust GWP42003-P/placebo or the CLB or other AEDs after discussion with the medical monitor.

The use of rescue medication is allowed if necessary. The use of oxygen may be considered as rescue medication if used as required. Any medication, other than the IMP, taken during the study must be recorded on the Case Report Form (CRF).

Any non-pharmacological therapies (e.g., ketogenic diet, VNS) must also be stable up to four weeks prior to baseline and throughout the duration of the study.

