8.3 Prohibited Therapy During Study Period

The following medications are prohibited for the duration of the study starting from acquisition of patient consent. However, any patients taking these medications after screening should not be withdrawn from the study unless there are safety concerns. If applicable, the possible effects of these medications on the primary endpoint will be considered.

- Any new medications or interventions for epilepsy (including ketogenic diet and VNS) or changes in dosage.
- Patients should not take any more than three AEDs inclusive of CLB.
- Recreational or medicinal cannabis or synthetic cannabinoid based medications (including Sativex) within three months prior to or during the study.

If any other IMP is taken as part of a clinical trial within twelve weeks of the screening visit or during the study, the patient must be withdrawn from this study.

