9.1.5 Concomitant Medication

Details of all current and recent medication (i.e., taken within the previous 28 days) including AEDs will be recorded at the screening visit (Visit 1) and reviewed at each subsequent visit. AEDs used during the study should be maintained at a stable dose. Any changes in concomitant medication during the study must be recorded in the CRF at study visits. Patients should stop taking any prohibited therapy prior to the screening visit, as defined in [Section 8.3](#).

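### Section 4.1 words the 30 mg/kg/day OLE maximum as covering other AEDs, and sections 8.3 and 9.1.5 conflict with 4.1, 6.1.6, 8.1 and 8.2 on whether AED doses may change in the OLE

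*Protocol*

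**What the plan says.** All references are to the current text, Protocol version 2.

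- **4.1 Study Design:** "Upon entry into the OLE the dose of GWP42003-P and other AEDs may be adjusted up or down to a maximum of 30 mg/kg/day".
- **3.3.1 Selection of Study Doses:** "During the OLE doses may be adjusted up or down, dependent on investigator opinion, to a maximum daily dose of 30 mg/kg GWP42003-P". The Study Design row of the synopsis and section 8.1.2 likewise name GWP42003-P alone when they give this figure.
- **8.2 Concomitant Therapy:** doses of concomitant AEDs, clobazam included, "must remain stable throughout the blinded phase of the study". Inclusion criterion 6.1.6 sets the same period, and 8.1 holds clobazam at its screening dose for the blinded phase.
- **8.3 Prohibited Therapy:** "The following medications are prohibited for the duration of the study starting from acquisition of patient consent". The first item on the list is "Any new medications or interventions for epilepsy (including ketogenic diet and VNS) or changes in dosage".
- **9.1.5 Concomitant Medication:** "AEDs used during the study should be maintained at a stable dose".

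**The concern.** Two instructions to sites do not fit together. The dose maximum in the design section is worded to apply to drugs for which no other section uses it. Separately, the protocol both permits and prohibits a change of AED dose during the OLE.

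The second matters more in practice. Patients who received placebo take GWP42003-P together with clobazam for the first time in the OLE. For all entrants, the GWP42003-P dose may then rise above the 20 mg/kg/day of the blinded phase. The study exists because an interaction with clobazam is suspected (3.3 and 3.4), so sites will plausibly have to ask whether clobazam or another AED may be changed. About seven centers are expected (4.2). One may change a dose on the strength of 4.1 and 8.2, while another holds it, or treats the same change as prohibited, on the strength of 8.3. Adverse events and seizures are to be summarized for the OLE, and those summaries would then reflect, in part, which section each site had read.

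**Working it through.** The plan has no calculation to reproduce here. The check sets the current passages side by side.

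**Step 1. Which drug does the 30 mg/kg/day maximum govern?**

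| Place | Drug to which the figure is attached |
|---|---|
| Synopsis, Study Design | GWP42003-P |
| 3.3.1 | GWP42003-P |
| 4.1 | GWP42003-P and other AEDs |
| 8.1.2 | GWP42003-P |
| 9.2.1.4.2 (Visit 4, Day 34) | GWP42003-P by context, since the change starts from the 20 mg/kg/day maintenance dose |

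In 4.1 one verb and one maximum serve both drugs, so the grammar extends the maximum to AEDs. No other place does so.

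**Step 2. Does the study include the OLE?** Yes. Section 4.1 opens by describing the study as a 34-day double-blind phase followed by an optional OLE of at most one year. A rule that runs for the whole study from consent therefore runs through the OLE.

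**Step 3. Is clobazam one of the AEDs?** Yes. Sections 6.1.6 and 8.2 name it among them, and 8.3 counts it within its limit of three AEDs.

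**Step 4. For how long must AED doses be stable?**

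| Section | Period or permission | OLE dose change |
|---|---|---|
| 4.1 | AEDs may be adjusted on OLE entry | allowed |
| 6.1.6 | AEDs including clobazam, blinded phase | not restricted |
| 8.1 | Clobazam at its screening dose, blinded phase | not restricted |
| 8.2 | AEDs including clobazam, blinded phase | not restricted |
| 8.3 | Dosage changes prohibited from consent, whole study | prohibited |
| 9.1.5 | Stable during the study, no phase named | not allowed for |

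Four sections point one way and two the other.

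**Step 5. Does any clause settle it?**

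- The exception in 8.2 covers only suspected interaction toxicity, after discussion with the medical monitor. It does not reach an ordinary OLE adjustment.
- Section 8.1.2 asks that other AED changes be reviewed with the medical monitor. That sentence stands in the paragraph on titration and adverse events during titration. It presupposes that changes occur but does not lift the prohibition in 8.3.
- Section 8.3 says that a patient who takes a listed therapy should stay in the study unless there are safety concerns. This softens the consequence of a breach and leaves the prohibition standing.
- Section 9.1.5 goes on to require that medication changes be recorded. Recording a change does not permit it.

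**Step 6. How far does it reach?** Enrollment is 20 patients, randomized 4:1, so 20 × 4/5 = 16 receive GWP42003-P and 20 × 1/5 = 4 receive placebo. If all continue, the conflict applies to 20 patients, of whom about 4 meet the combination for the first time in the OLE. The PK profiles start on Day 1 and Day 33, with the last sample on Day 34 taken before the OLE begins. The primary PK comparison therefore does not depend on the OLE rule.

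**The case against.** The best defence is that this is a drafting slip whose intent is easy to recover. Section 4.1 itself sends readers to Section 8 for treatment detail, and 8.1.2 gives the maximum for GWP42003-P alone. On stability, 6.1.6, 8.1 and 8.2 agree on the blinded phase, and clobazam is an investigational product only in that phase. What remains is one bullet in 8.3 and a sentence in 9.1.5 that says should, not must. The OLE is also uncontrolled, and its GWP42003-P dose already varies at the investigator's discretion, so AED changes would be only one further source of variation.

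Much of this stands. It limits the consequence and shows that little text needs changing. It does not remove the conflict: 8.3 is the section a site consults on prohibited therapy, and its wording is explicit and has no phase limit.

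A reader might also infer more than the documents support:

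- **That clobazam could be raised to 30 mg/kg/day.** At the 70 kg used in 3.3.1 this would be 30 × 70 = 2,100 mg/day. Nothing suggests that a site would act on it. Clobazam is the patient's own supply, taken as the physician advises. The 20 mg/day in 6.2.2 is an entry exclusion, not an on-study maximum, so a ratio of the two figures measures no real risk. The figure shows only that the sentence is badly worded.
- **That an OLE dose change is a defined protocol deviation.** The protocol contains no such definition. Section 13.3.3 says only that deviations will be listed.

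**Conclusion.** The point holds as an internal inconsistency with two parts. Section 4.1 words the OLE maximum to include other AEDs, against the synopsis, 3.3.1 and 8.1.2. The protocol also gives opposing rules on changing clobazam and other AEDs in the OLE: 4.1, 6.1.6, 8.1 and 8.2 on one side, 8.3 and 9.1.5 on the other.

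It concerns up to 20 patients for up to one year, on the assumption that all enter the OLE. The effect is on consistent OLE conduct and on the reading of OLE safety and seizure summaries. How many patients would in fact have an AED change cannot be told from the protocol. It would be wrong to infer that the interaction result is at risk, because both PK assessments precede the OLE. It should be corrected because these are operative, safety-relevant instructions and the correction is cheap. No view is taken here on which dose maximum or AED rule is right.

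**What to change.** 1. Reconcile the sentence in 4.1 with the synopsis, 3.3.1 and 8.1.2 so that it is clear which drug the 30 mg/kg/day maximum governs. Put any statement about other AEDs in the OLE in a separate sentence.
2. Reconcile 4.1, 6.1.6, 8.1, 8.2, 8.3 and 9.1.5 so that all six state the same period for AED stability, clobazam included.
3. The sponsor and the medical monitor decide which rule applies in the OLE; the text then follows that decision.

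The cost is amendment wording. Sample size, visits, procedures and the primary analysis do not change.

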4.1.1 Primary Endpoint

The primary endpoints of the study are the PK parameters (C_{max} , t_{max} , $AUC_{(0-\infty)}$, $AUC_{(0-t)}$, $t_{1/2}$) of the following analytes:

- CLB
- N-CLB
- CBD
- CBD major metabolites

4.1.2 Secondary Endpoint(s)

To assess the safety and tolerability of GWP42003-P compared with placebo when taken in combination with CLB. Safety and tolerability will be assessed using the following parameters:

- AEs
- 12-lead Electrocardiogram (ECG)
- Clinical laboratory parameters (clinical chemistry, hematology and urinalysis)
- Vital signs
- Columbia-Suicide Severity Rating Scale (C-SSRS)
- Seizure Frequency
- Abuse Liability

PK parameters (C_{max} , t_{max} , $AUC_{(0-\infty)}$, $AUC_{(0-t)}$, $t_{1/2}$) of the following analytes:

- THC
- THC major metabolites

4.2 Number of Centers

An estimated number of seven centers are expected to participate in this study.

4.3 Number of Patients

A total of 20 patients will be enrolled into the study. Recruitment for the study will be competitive between participating sites.

The sample size calculation is explained fully in [Section 13.1](#).

5. INVESTIGATIONAL MEDICINAL PRODUCT

Please refer to the separate Pharmacy Manual for more detailed information on the IMP.

5.1 GWP42003-P Oral Solution

GWP42003-P oral solution is presented as a pale yellow oily solution containing 100 mg/mL CBD dissolved in the excipients sesame oil and anhydrous ethanol with added sweetener (sucralose) and strawberry flavoring [Table 5.1-1](#).

Table 5.1-1 Formulation of GWP42003-P Oral Solution

Material	Quantity
CBD	100 mg/mL
Anhydrous ethanol	79 mg/mL
Sucralose	0.5 mg/mL
Strawberry flavoring	0.2 mg/mL
Sesame oil	make up to 1 mL

5.2 Placebo Oral Solution

Placebo oral solution contains the excipients sesame oil and anhydrous ethanol with added sweetener (sucralose) and strawberry flavoring [Table 5.2-1](#).

Table 5.2-1 Formulation of Placebo Oral Solution

Material	Quantity
Anhydrous ethanol	79 mg/mL
Sucralose	0.5 mg/mL
Strawberry flavoring	0.2 mg/mL
Sesame oil	make up to 1 mL

5.3 Packaging, Storage and Drug Accountability (Cannabidiol/Placebo)

5.3.1 Packaging and Labelling

The IMP will be manufactured and packaged by GWP. It will be distributed by GWP or delegated contractors. The IMP will be presented in 100 mL amber glass bottles with child-resistant caps and packed in cartons. Sufficient IMP will be dispensed at each visit considering the weight of each patient. A unique pack identification number will be used to identify each box and the medication it contains. The pack numbers will cross check with the batch numbers held at GWP. GWP will ensure that all IMP provided is fully labelled and packaged. Label text will comply with European Union (EU) guidance on Good Manufacturing Practice, Annex 13 Labelling and will be fully described in the separate Pharmacy Manual. In addition, any local country requirements in accordance with local drug law or regulatory requirement will be included in the final label text.

Directions of use, name, address and telephone number of investigator, or main contact for information about the product or the clinical trial, will be provided separately to the patient.

5.3.2 Storage

The IMP must be stored upright at room temperature (< 30°C) and must not be refrigerated or frozen. It must also be kept away from heat and direct sunlight.

The IMP must be stored in compliance with the local regulations for a controlled drug (if applicable to country). The sponsor must approve storage location and facilities.

Should storage conditions deviate from these specified requirements, the GW study monitor should be contacted immediately to confirm if the IMP remains suitable for use. IMP should be placed under quarantine until confirmation is received that IMP is suitable for use.

Temperature records of the storage location must be maintained on a daily basis (a minimum of Monday–Friday, excluding public holidays) from date of receipt of first shipment until end of study dispensing period at each site. These records must contain at least the minimum and maximum daily temperatures and should be made available to the appropriate GW personnel for review throughout the study.

5.3.3 Supply and Return of Investigational Medicinal Product

Once a site has been activated at study initiation, IMP will be shipped to a responsible person, such as the pharmacist, at the investigator's center, who will check the amount received and the condition of the drug. Details of the IMP received will be recorded in the IMP accountability record. The site will acknowledge IMP receipt and will complete any receipt forms required. IMP will be dispensed and returned as detailed in [Section 5.3.4](#) with further IMP shipments to be requested as necessary. As directed, all supplies, including unused, partially used, or empty containers, will be returned to GWP or destroyed at the center if agreed in writing by the study monitor.

5.3.4 Investigational Medicinal Product Accountability

The investigator has overall responsibility for the accountability of all used and unused IMP. A drug accountability record for the IMPs must be kept current and should contain:

- The dates and quantities of IMP received from GWP.
- Patient's identification.
- Date and quantity of IMP dispensed.
- The initials of the dispenser.

- Date and quantity of IMP returned to the investigator/pharmacy.

A record of returned IMP must be completed and included in the shipment of used and unused IMP to GWP. At the end of the study a record/statement of reconciliation must be completed and provided to GWP.

These inventories must be made available for inspection by authorized GW or GWP representatives and local officials or regulatory agency inspectors.

Please refer to the separate Pharmacy Manual for more detailed information on the IMP.

